5.5.14 Early study termination

The study can be terminated at any time for any reason by Novartis. Should this be necessary, the patient should be seen as soon as possible and treated as a patient prematurely withdrawn from the study. The investigator may be informed of additional procedures to be followed in order to ensure that adequate consideration is given to the protection of the patient's interests. The investigator will be responsible for informing the Institutional Review Board/Independent Ethics Committee (IRBs/IECs) of the early termination of the trial.

6 Visit schedule and assessments

Table 6-1 lists all of the assessments and indicates with an "x" when they are to be performed. Patients should be seen for all visits on the designated day within the recommended "visit window" specified below, or as close to it as possible. The site should make every effort to help bring the patients to the clinic visits, including providing transportation if necessary. If any visits are delayed or missed, the site personnel should ensure alignment of future patient visits according to the originally planned visit schedule (i.e. rescheduled visit window needs to be calculated with reference to first dose received; day of randomization and first dose received may differ occasionally), and should ensure that 2 consecutive infusions are done at least 14 days apart.

Recommended visit windows:

Randomization/Day 1: + 2 days

Weeks 4-12: +/- 4 days

Weeks 16-24: +/- 7 days

Weeks 36-48: +/- 14 days

Some of the following principles should be taken into consideration when scheduling a visit:

- Assessments for a particular visit - including the randomization visit - may be split over several days.
- [REDACTED] physical performance tests should be considered early in the visit to avoid physical or mental exhaustion of the patient.
- Laboratory work in particular those requiring 8 hours fasting should be done early in order to allow the patients to eat and drink
- Patient dosing should be the last procedure to be performed

During the treatment epoch, patients may be seen at unscheduled visits for instance for AEs that in the opinion of the investigator need intervention or repeated laboratory testing. All relevant safety assessments may be performed as deemed necessary by the investigator. During these unscheduled visits, investigational treatment must **NOT** be administered.

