6.5.7 X-ray assessment of surgical procedure

A historical X-ray done by local practice during or after surgery (in some cases prior to the initiation of screening) will be used by the investigator for eligibility assessment. The summary of the local assessment will be recorded in the Perioperative eCRF and must confirm adequate surgical execution of internal fixation or arthroplasty for fracture repair. Images do not need to be submitted to the central reader vendor.

During the trial, an X-ray of the operated hip will be taken at Week 24 (EoT) visit - as indicated in [Table 6-1](#) - to assess whether fracture healing has been completed (bone union) and whether there are any potential late complications of the surgery. If bone-union is not achieved at Week 24, patient will be followed up at Week 36 and also potentially at Week 48 (EoS), if bone union is still not achieved at Week 36. Additional unscheduled X-rays may also be required if there is any clinical suspicion of delayed/improper fracture healing. Any findings on X-ray need to be reported as adverse events. Specifically, bone non-union seen at Week 36 (delayed fracture healing) needs to be reported as an SAE.

All scheduled and unscheduled X-rays performed after enrollment will be transferred to a central reader (details provided in *Imaging Manual*). Two independent readers of the assigned

vendor will perform a blinded assessment of the images for bone union and a number of pre-specified orthopedic complications. In case of discordant medical opinions regarding the presence or absence of these complications, a third reader will settle a final decision. The central reader may request sites to provide additional X-rays, if available, to support overall assessment of the specific finding.

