7.2 Serious adverse events

7.2.1 Definition of SAE

An SAE is defined as any adverse event (appearance of (or worsening of any pre-existing) undesirable sign(s), symptom(s) or medical conditions(s) which meets any one of the following criteria:

- is fatal or life-threatening
- results in persistent or significant disability/incapacity
- constitutes a congenital anomaly/birth defect
- requires inpatient hospitalization or prolongation of existing hospitalization, unless hospitalization is for:
 - routine treatment or monitoring of the studied indication, not associated with any deterioration in condition (specify what this includes)
 - elective or pre-planned treatment for a pre-existing condition that is unrelated to the indication under study and has not worsened since signing the informed consent
 - treatment on an emergency outpatient basis for an event not fulfilling any of the definitions of a SAE given above and not resulting in hospital admission
 - social reasons and respite care in the absence of any deterioration in the patient's general condition
- is medically significant, i.e. defined as an event that jeopardizes the patient or may require medical or surgical intervention.

Life-threatening in the context of a SAE refers to a reaction in which the patient was at risk of death at the time of the reaction; it does not refer to a reaction that hypothetically might have caused death if more severe (see Annex IV, ICH-E2D Guideline).

All malignant neoplasms and delayed fracture healing (i.e. bone non-union seen at X-ray at W36 or later) will be assessed as serious under “medically significant” if other seriousness criteria are not met.

Medical and scientific judgment should be exercised in deciding whether other situations should be considered serious reactions, such as important medical events that might not be immediately life threatening or result in death or hospitalization but might jeopardize the patient or might require intervention to prevent one of the other outcomes listed above. Examples of such events are intensive treatment in an emergency room or at home for allergic bronchospasm, blood dyscrasias or convulsions that do not result in hospitalization or development of dependency or abuse (see Annex IV, ICH-E2D Guideline).

Any suspected transmission via a medicinal product of an infectious agent is also considered a serious adverse reaction.

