9.5.2.3 Adverse events

Treatment emergent adverse events (events start after the first dose of investigational treatment or events present to the first dose of investigational treatment but increased in severity) will be summarized by primary system organ class, preferred term and treatment.

Incidence of potential cases of safety risks as defined in the case retrieval strategy with frequency counts by treatment arm and estimated rates with corresponding 95% confidence intervals regardless of investigational treatment relationship will be provided to compare each of bimagrumab treatments with placebo group.

Separate summaries will be performed for study medication related events, death, serious adverse events, adverse events leading to discontinuation of the investigational study drug , and other adverse events of interest.

Additional analyses utilizing the beta binomial model may be used to summarizing absolute rates by treatment group in the case of sparse data or if it is clinically warranted. The beta binomial model will utilize a non-informative beta (1/3, 1/3) prior. Summaries may include posterior probabilities for a clinically relevant difference(s), point estimates under the posterior distribution with corresponding 95% credible intervals (i.e., equal tail) and/or a graphical presentation of the entire posterior distribution itself.

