2.11.1 General adverse events

Adverse events will be categorized based on date of onset or worsening relative to the first and last infusion of study drug as:

- Pre-treatment: Date of onset or worsening of the AE is prior to the start of first infusion of study drug.
- Treatment-emergent: Date of onset or worsening of the AE is on or after the start of the first infusion of study drug until the last infusion of study drug (expected per protocol at Week 20) + 56 days (see [Section 2.3](#) [Treatment pooling and data handling of pre-amendment 2] for more details).
- Post-treatment: Date of onset or worsening of the AE is after the date of last infusion of study drug (expected per protocol at Week 20) + 56 days.

Missing or incomplete AE onset dates will be imputed prior to categorization; algorithms for date imputations will be provided in RAP Module 8 (Programming Specifications). No imputation will be applied to AE end dates. Hence, if the end date is missing, the duration of the AE will be “continuing”.

All AEs reported will be listed. With the exception of the overview presentations, primarily only TEAEs/Post-treatment AEs will be summarized for each treatment group and across active bimagrumab treatment groups combined (“Active Total: Safety” - Includes bimagrumab 700 mg, bimagrumab 210 mg and bimagrumab 70 mg), overall and by region (Japan/Non-Japan) (see [Section 2.6](#) [Subgroups]). Percentages (%) will be derived relative to the number of patients “at risk” (in SAF analysis set or ongoing at the start of follow-up). At the time of the primary analysis number of patients “at risk” comprises:

- Incidence of AEs at Screening: All enrolled patients implying all patients who provided informed consent.
- Incidence of AEs in treatment: Patients assigned to the SAF analysis set regardless of study status, implying all patients entering the 24-week treatment epoch.
- Incidence of AEs in post-treatment follow-up:
 - Patients who completed treatment but are ongoing in post-treatment follow-up or who have discontinued during post-treatment follow-up.
 - Patients who prematurely discontinue treatment within the defined 24-week treatment epoch and who then continue study participation as part of the planned 4-week post-treatment follow-up.
 - Patients who completed treatment and post-treatment follow-up (study completed at the time of the primary analysis).

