- Carcinogenicity: Carcinogenicity [BYM338] (CMQ) (NMQ) [narrow].
- Abuse potential: Drug abuse, dependence and withdrawal (SMQ) [broad].
- Diarrhea - Diarrhea [BYM338] (CMQ) (NMQ) [narrow].

The following actual exposure-adjusted (rate in 100 person-years) treatment-emergent AESIs regardless of study drug relationship by risk search criteria level (based on the NMQs or MedDRA SMQs) will be summarized for each treatment group and “Active Total: Safety”, overall and by region (Japan/Non-Japan) (see [Section 2.6](#) [Subgroups]). Percentages (%) will be derived relative to the number of patients “at risk” (in SAF or ongoing at the start of follow-up).

Additional data for adverse events of special interest (AESIs) related to liver, diarrhea spontaneous muscle contractions, orthopedic and heart/cardiomyopathy complications will be recorded, by the investigators, in the Liver event - overview eCRFs, Diarrhea or diarrhea-like

events eCRF, Spontaneous muscle contractions eCRF, Orthopedic complication eCRF, Heart failure eCRF and Cardiomyopathy eCRF respectively. This patient information will be summarized descriptively for all patients assigned to SAF analysis set, or who are ongoing at the start of follow-up (“at risk”).

Liver events

For treatment-emergent and post-treatment liver events, descriptive statistics (see [Section 3.2](#) [Precision and summary statistics]) will be presented based on high-level information in the Liver event – overview eCRF, Liver event - history of alcohol use 6 weeks prior to liver event eCRF and Liver event - drugs of abuse history eCRF:

- Number of treatment-emergent and post-treatment liver events (E).
- Type of liver injury:
 - Acute.
 - Acute on chronic liver disease.
 - Chronic.
- Liver failure present (yes/no).
- Tattoos in the last year (yes/no).
- Was the liver injury associated with any clinical signs/symptoms (yes/no).
- Any reasonable possibility that the liver event is related to study drug:
 - No.
 - Yes, investigational treatment.
 - Yes, other study drug (non-investigational).
 - Yes, both and/or indistinguishable.
- Did the patient discontinue study drug (yes/no).
- History of alcohol use (based on a “yes” response to the question, “Did subject use alcohol within the last 6 weeks?” on the History of alcohol use 6 weeks prior to liver event eCRF) presenting the amount of consumed alcohol (on average) by the following categories:
 - < 1 drink per day.
 - ≥ 1 to ≤ 2 drinks per day.
 - > 2 to ≤ 3 drinks per day.

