* For pre-amendment 2 patients, cut-off at Week 20 + 56 days. ** For patients who discontinued during treatment epoch, the target visit day values are EOT (derived) + 84 days and EOT (derived) + 168 days for Week 36 and Week 48, respectively. In addition, for the discontinued patients, the start day of the Week 48 visit name is 1 day after last infusion of study drug + 56 days (for pre-amendment 2 patients, cut-off at Week 20) + 126 days.

Realignment per assessment type (not following the general realignment of visits) is presented in Tables 3.2 to 3.7 below:

Table 3.2 Laboratory: Hormones /ECG

Study Epoch	Visit Name	Target Visit Day	Start Day of Visit Window	End Day of Visit Window
Screening	Screening	Day -39 to -1		
Treatment	Day 1	Day 1		
	Baseline	Defined as the last available assessment (scheduled or unscheduled) prior to the start of the first infusion of study drug, including pre-dose assessments at Day 1.		
	Week 12	Day 84	2	126

	Week 24	Day 168	127	Last infusion of study drug + 56 days *
	End of Treatment (derived)	End of Treatment is defined as the last available assessment (scheduled or unscheduled) assigned to treatment and including the 56-days *.		
Post-treatment Follow-up	Week 48	336**	1 day after last infusion of study drug + 56 days *	Last known date in study
	End of Study (derived)	End of Study is defined as the last available assessment (scheduled or unscheduled) assigned to the study.		

* For pre-amendment 2 patients, cut-off at Week 20 + 56 days. ** For patients who discontinued during treatment epoch, the target visit day values are EOT (derived) + 168 days at Week 48.

Table 3.3 Safety Laboratory: Hematology/Chemistry/Urinalysis

Study Epoch	Visit Name	Target Visit Day	Start Day of Visit Window	End Day of Visit Window
Screening	Screening	Day -39 to -1		
Treatment	Baseline	Defined as the last available assessment (scheduled or unscheduled) prior to the start of the first infusion of study drug, including pre-dose assessments at Day 1.		
	Week 4	Day 28	1	42
	Week 8	Day 56	43	70
	Week 12	Day 84	71	126
	Week 24	Day 168	127	Last infusion of study drug + 56 days *
	End of Treatment (derived)	End of Treatment is defined as the last available assessment (scheduled or unscheduled) assigned to treatment and including the 56-days *.		
Post-treatment follow-up	Week 48	336 **	Last infusion of study drug + 56 days * + 1 day	Last known date in study

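### The exposure-adjusted bone-healing rate stops 56 days after the last infusion, so it leaves out non-union dated at the Week 36 or 48 X-ray, and no unconditional whole-study comparison fills the gap

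*SAP*

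**What the plan says.** **Treatment-emergent.** Protocol 9.5.2.3 gives a start rule only: "events start after the first dose of investigational treatment or events present to the first dose of investigational treatment but increased in severity". SAP 2.3 and 2.11.1 add an end. An event counts if its onset or worsening falls between the first infusion and a limit, "until the last infusion of study drug (expected per protocol at Week 20) + 56 days"; anything later is post-treatment. For patients randomized before Amendment 2, the visit-window footnotes in SAP 3.5.1 hold the same limit: "For pre-amendment 2 patients, cut-off at Week 20 + 56 days". SAP 2.14, which lists departures from the protocol, mentions a change to epoch presentation but not this end date.

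**The rate table.** SAP 2.11.6 lists the AESIs, including effects on bone fracture healing, selected by a MedDRA query. It then plans "The following actual exposure-adjusted (rate in 100 person-years) treatment-emergent AESIs regardless of study drug relationship by risk search criteria level".

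**Delayed healing.** Protocol 6.5.7 schedules a hip X-ray at Week 24, repeats it at Week 36 (and Week 48 if needed) only when union is incomplete, allows unscheduled films on clinical suspicion, and makes any X-ray finding a reportable adverse event. It adds that "bone non-union seen at Week 36 (delayed fracture healing) needs to be reported as an SAE". Protocol 7.2.1 agrees, describing "delayed fracture healing (i.e. bone non-union seen at X-ray at W36 or later".

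**Orthopedic events.** Protocol 9.5.2.2 plans frequency counts, with contrasts as odds ratios and/or risk differences and 95% CIs, depending on how rare the event is. SAP 2.11.6 handles orthopedic events like cardiac events. Frequencies are tabulated for treatment-emergent and post-treatment events, but odds ratios and time to first event are planned only if events reach 10%. It expects orthopedic events to be rare.

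**The concern.** Fracture healing is the protocol's own stated reason for X-ray follow-up (6.5.12), because this is the first use of the drug after major hip-fracture surgery. The rate table is where the SAP puts fracture-healing events over person-time. If its window closes before the visit at which the protocol first calls non-union delayed healing, a difference between arms that first appears at Week 36 will not show there. A sparse row under a fracture-healing label could then be taken as reassurance when it partly reflects the window.

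The later events are tabulated, but apart from the on-treatment ones and on different denominators. The analyses that would compare arms over the whole study have an event threshold that a rare complication may not reach.

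**Working it through.** **Inputs.** SAP Table 3.1 puts Week 20 at Day 140, Week 24 at Day 168, Week 36 at Day 252 and Week 48 at Day 336. Protocol section 6 gives the visit windows: "Weeks 16-24: +/- 7 days", and plus or minus 14 days for Weeks 36 to 48. The plan prints no day for the end of the treatment-emergent window, so there is no stated figure to reproduce. The grid itself is consistent: the Week 48 window start is 252 + 42 + 1 = 295, as printed, and the midpoint rule (252 + 336)/2 + 1 also gives 295.

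**Where the window closes, for a patient given all six doses**
- Nominal: 140 + 56 = Day 196.
- With the visit window: 133 + 56 = 189 to 147 + 56 = 203.
- Share of the scheduled study: 196/336 = 58%.

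**Where the films fall**
- Week 24: 168 ± 7 = Day 161 to 175, inside the window even at its earliest close (Day 189).
- Week 36: 252 ± 14 = Day 238 to 266, outside it.
- Gap: nominally 252 − 196 = 56 days; at the least 238 − 203 = 35 days.
- For a Day 238 film to fall inside, the last infusion would have to be on Day 238 − 56 = 182 or later.

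**What the onset date does to the rate.** Assume 70 patients in an arm, full follow-up and six doses exactly 28 days apart, so that the last infusion is 140 days after the first. The SAP exposure formula then gives 140 + 56 + 1 = 197 days. (Placing the last dose on Day 140 gives 196 days and changes the per-event rate only from 2.65 to 2.66.)
- Treatment-emergent person-time: 70 × 197/365.25 = 37.75 person-years; one event is 100/37.75 = 2.65 per 100.
- Whole-study person-time: 70 × 336/365.25 = 64.39 person-years; one event is 100/64.39 = 1.55 per 100.

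| Assumed non-unions in the arm | Planned rate, dated at Week 36 | Planned rate, dated at Week 24 | Whole-study rate |
|---|---|---|---|
| 1 | 0 | 2.65 | 1.55 |
| 2 | 0 | 5.30 | 3.11 |
| 4 | 0 | 10.59 | 6.21 |
| 7 | 0 | 18.54 | 10.87 |

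The event counts are assumptions; the documents give no expected non-union rate. Person-time is an upper bound, since protocol section 4 expects only about 120 of 245 patients to finish 48 weeks. The same patients can contribute nothing or everything to the planned rate, depending on a dating rule that neither document states.

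**The 10% condition.** The SAP does not say whether 10% is per arm or pooled. Per arm of 70 it needs 7 patients; over 245 it needs 0.10 × 245 = 24.5, so 25. With assumed rates of 5% and 10% in two arms of 70, the pooled proportion is (3.5 + 7)/140 = 7.5%, below the threshold on a pooled reading.

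**The case against.** A reader might infer that delayed healing can never enter the bone-healing rate, or that its capture is 0%. The documents do not support that.

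- The SAP dates events by onset or worsening, not by when they become serious. A scheduled Week 36 film follows incomplete union at Week 24, and any X-ray finding is reportable, so a site could date onset at Day 161 to 175, inside the window.
- The AESI is chosen by a MedDRA query whose terms are not in the documents. Terms from a Week 24 or unscheduled film may qualify.

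Nor are later events lost. Orthopedic AESIs are tabulated for post-treatment events (SAP 2.11.3), serious events likewise (2.11.2, 2.11.5), and all adverse events by interval, including Day 181 to 270 and Day 271 to End of Study. Orthopedic frequencies cover both periods without condition. X-ray non-union is summarized by visit if there are enough films (2.11.11). SAP 3.11.8 describes the orthopedic odds ratio without repeating the 10% condition, and an external DMC watches for delayed healing.

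The protocol is also silent on an end date rather than opposed to one. It leaves detail to the SAP, and its own exposure formula (9.1.1) uses the same 56 days, so aligning events with exposure is a reasonable choice.

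All of this stands, and it limits the point to one rate and one missing comparison. It does not remove either. The post-treatment tables separate the events from the on-treatment ones, and 2.11.6 makes the joint analyses conditional. Protocol 9.5.2.2 does qualify its contrasts by rarity, but this reads most naturally as choosing the measure, not as a 10% rule for dropping the contrast.

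**Conclusion.** The point holds in a limited form. The exposure-adjusted bone-healing rate covers about 58% of the scheduled study and omits non-union whose onset or worsening is dated at the Week 36 or 48 film, at least 35 days after the window closes. Non-union dated earlier can count, and later events are reported elsewhere. What the plan lacks is a single whole-study comparison between arms that is produced whatever the number of events.

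This rests on the last infusion and the Week 36 film falling within their visit windows, and on dating at the later film. It mainly concerns completers: under the Table 6-1 footnote, a patient who stops treatment early has the End of Study visit about 28 + 28 = 56 days after the last dose, so would not normally have a Week 36 film.

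The absence of the end date from SAP 2.14 is a lesser matter of documentation. No efficacy result is affected. This is a worthwhile, inexpensive improvement to the reporting of a named risk.

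**What to change.** 1. In SAP 2.11.6, add a first-infusion-to-End-of-Study rate for the bone-healing AESI and for orthopedic events, with time on study as the person-time. Split it within the table by on-treatment and follow-up onset.
2. Give the contrast of each dose with placebo, with its 95% CI as in protocol 9.5.2.2, without the 10% condition. Align 2.11.6 and 3.11.8 on this.
3. State which onset date applies when incomplete union at Week 24 becomes non-union at Week 36. As written, such an event could be treatment-emergent by onset and post-treatment by worsening.
4. Name the 56-day end of treatment-emergent in SAP 2.14.
5. Clarify the denominator of the existing rate table, whose text also mentions patients ongoing at the start of follow-up. Check too that person-time matches the event cut-off for the 14 pre-Amendment 2 patients, whose actual exposure can run beyond it.

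The cost is SAP wording and one added or reprogrammed table; no new data are needed. A whole-study rate mixes on-drug and off-drug time, which the split makes visible, and it would be complete only at the final update analysis.

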9.5.2.1 Cardiac Safety Analysis

The frequency of experiencing at least one cardiac event of special interest (AESI) – cardiomyopathy, ischemic heart disease, heart failure, or cardiac rhythm disturbances (brady/tachyarrhythmias) - will be summarized by treatment group. In addition, the relative risk (to placebo) of experiencing at least one AESI (based on the confirmed events) will be calculated with 95% confidence intervals for each of the bimagrumab treated groups versus placebo. The results of these analyses will be presented in tabular form. If a substantial number of events occur, data may also be summarized graphically using adverse events dot plots (incidences and relative risks) per experimental dose.

Depending on the rarity of the events, a Kaplan-Meier plot for time-to-the first event with a censored adjusted median time and corresponding 95% confidence intervals may be presented for each treatment group. Differences between placebo and each of the bimagrumab treated groups will be further assessed by a log-rank test if the Kaplan-Meier plots provide a clinically warranted rationale.

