9.5.2.2 Bone Safety Analysis

The incidence of orthopedic complications (i.e. with focus on bone non-union as per X-ray imaging) will be summarized through frequency counts by treatment group. The treatment contrasts will be presented as odds ratios and/or absolute risk differences with corresponding 2-sided 95% confidence intervals depending on the rarity of the event.

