 - During or shortly after an exercise session.
 - In bed and not yet asleep.
 - Asleep.
- The existence of pain or not during the contraction (yes/no).
- The association of the contraction:
 - Uncontrolled movement of joint(s).
 - Abnormal bending of the affected joint(s).
 - Inability to open or relax hands after making a fist.
- The part of the body that was affected:
 - Head/face (yes/no).
 - Chest or ribcage (yes/no).
 - Back (yes/no).
 - Abdomen (yes/no).
 - Back of the thigh (yes/no).
 - Front of the thigh (yes/no).
 - Calf (yes/no).
 - Feet (yes/no).
 - Arms (yes/no).
 - Hands (yes/no).
 - Other (yes/no).
- If the event stopped spontaneously ([yes/no], if “no” then were any of the following medications or non-drug therapies administered to treat the event?):
 - Stretching and massaging (yes/no).
 - Hydration (yes/no).
 - Heat/cold (yes/no).
 - Analgesics (yes/no).
 - Muscle relaxant agent (yes/no).
 - Other (yes/no).

Percentages (%) will be derived relative to the total number of muscle contraction events (E) with data available per question.

Cardiac safety events

The frequency of patients experiencing at least one treatment-emergent or post-treatment cardiac event (cardiomyopathy, ischemic heart disease, heart failure, or cardiac rhythm disturbances [brady/tachyarrhythmias]) will be summarized in separate tables for each treatment group and “Active Total: Safety”, overall and by region (Japan/Non-Japan) (see [Section 2.6](#) [Subgroups]). Percentages (%) will be derived relative to the number of patients “at risk” (in SAF analysis set, or who are ongoing at the start of follow-up).

If the number of cardiac safety events are sufficient (based on events confirmed ($\geq 10\%$), the odds ratio, associated 95% confidence interval and p-value for the difference between each of the active bimagrumab treatment groups as well as “Active Total: Safety” and placebo will be analyzed using PROC FREQ. This analysis will be based on the proportion of patients with at least one treatment-emergent or post-treatment cardiac event (based on events [E] confirmed by adjudication committee) (see [Section 3.11.8](#) [Odds ratios]). Incidence calculations will be based on the number of patients with at least one cardiac safety event relative to the number of patients in SAF analysis set, or who are ongoing at the start of follow-up (“at risk”).

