In addition, provided again that there are a sufficient number of events ($\geq 10\%$ of patients have at least one event), the time to the first cardiac event over the course of the study (as calculated relative to the start of first infusion of study drug) will be estimated for each treatment group and “Active Total: Safety”. Kaplan-Meier estimates for median time to first cardiac event with 95% confidence interval, 25th and 75th percentiles will be presented. Patients not experiencing a cardiac event will be censored at the time of study completion, premature discontinuation or if ongoing in the study at the last available assessment date. The survival distributions of time to first cardiac event will be compared between each active bimagrumab treatment group, “Active Total: Safety” and placebo by means of the log-rank statistic (see [Section 3.11](#) [Statistical methodology and assumptions]).

As the number of cardiac rhythm disturbance, heart failure, ischemic heart disease and cardiomyopathy events are expected to be low, descriptive statistics (see [Section 3.2](#) [Precision and summary statistics]), will be performed on the questions listed in the Cardiac rhythm disturbances, Heart failure, Ischemic heart disease and Cardiomyopathy eCRFs. Any information recorded in the Adverse events eCRF for an AE which is deemed to have an AE classification of “Cardiac rhythm disturbances”, “Heart failure”, “Ischemic heart failure” or “Cardiomyopathy” will also be summarized descriptively, if relevant.

Orthopedic events

Orthopedic events (i.e. fracture healing complications) will be summarized in a similar manner as the cardiac safety events described above. These events are expected to be rare and orthopedic information is recorded in the Orthopedic complications eCRF.

Hospitalizations

Hospitalizations will be summarized in a similar manner as the orthopedic/cardiac safety events described above. Descriptive statistics (see [Section 3.2](#) [Precision and summary statistics]) will be presented for certain characteristics as recorded in the Hospitalization eCRF. These are:

- Number of patients hospitalized and number of hospitalization events (E).

- Reasons for hospitalization:
 - Injurious fall with fracture.
 - Other.
- Place of discharge:
 - Home.
 - Long-term care facility.
- Average duration of hospitalizations (days) = Duration of hospitalization (Date of discharge – date of admission) / Number of hospitalizations.

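### SAP 2.11.6 makes the cardiac contrast with placebo, and probably the orthopedic one, conditional on 10% events, in conflict with protocol 9.5.2.1 and SAP 3.11.8

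*SAP*

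**What the plan says.** **Protocol.** For cardiac events of special interest, section 9.5.2.1 states that "the relative risk (to placebo) of experiencing at least one AESI (based on the confirmed events) will be calculated with 95% confidence intervals", for each bimagrumab group against placebo. No event count is attached. In that section only the dot plots, the Kaplan-Meier display and the log-rank test depend on how many events occur. For orthopedic complications, section 9.5.2.2 states: "The treatment contrasts will be presented as odds ratios and/or absolute risk differences with corresponding 2-sided 95% confidence intervals". The sentence then ends with a qualifier about how rare the event is.

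**SAP 2.11.6.** Some output is unconditional: "The frequency of patients experiencing at least one treatment-emergent or post-treatment cardiac event" is summarized for each group, for all active groups combined and by region. The comparison with placebo is conditional: "If the number of cardiac safety events are sufficient" is followed by a bracket on confirmed events that gives a figure of at least 10% and is not closed, and then by the odds ratio, interval and p-value. The time-to-event analysis is planned "provided again that there are a sufficient number of events", and here the 10% is explicitly a share of patients. Orthopedic events "will be summarized in a similar manner as the cardiac safety events described above", and the SAP adds: "These events are expected to be rare". It also expects low numbers for the cardiac event types.

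**SAP 3.11.8.** The methods section derives odds ratios with 95% confidence intervals and p-values for the occurrence of at least one adverse event of special interest, one cardiac event and one orthopedic event. It uses an exact Fisher procedure and sets no threshold.

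**SAP 2.14.** The list of changes from the protocol mentions neither the 10% condition nor the move from relative risk to odds ratio for cardiac events.

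**The concern.** A minimum event count is reasonable for a survival curve. For a harm contrast it works the wrong way round: when events are few, the confidence interval shows how large an excess the trial has failed to exclude. A table of counts by arm does not show that.

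Both event classes matter in this trial. Protocol 9.5.2.2 makes bone non-union the focus of the bone analysis. Section 6.5.12 notes that bimagrumab had not been tested before in patients having major surgery for hip fracture. Routine echocardiography was dropped for patients enrolled after Amendment 3, which puts more weight on adjudicated cardiac events. If a programmer follows 2.11.6 as written, the contrast that the protocol specified for cardiac events would be missing in the very situation the SAP expects.

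**Working it through.** The 10% is a reporting rule, so the plan has no derived figure to reproduce. The check has three parts.

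**1. The sections side by side**

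| Source | Cardiac contrast | Orthopedic contrast | Threshold |
|---|---|---|---|
| Protocol 9.5.2.1 | Relative risk, 95% CI | – | None |
| Protocol 9.5.2.2 | – | Odds ratio and/or risk difference, 95% CI | None stated; rarity qualifier |
| SAP 2.11.6 | Odds ratio, 95% CI, p-value | By cross-reference to cardiac | 10%, no denominator |
| SAP 3.11.8 | Odds ratio, 95% CI, p-value | Odds ratio, 95% CI, p-value | None |

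The cardiac conflict is plain, both between protocol and SAP and within the SAP. The orthopedic threshold is an inference from the cross-reference.

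**2. How often the condition would be met**

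Inputs: planned N = 3 × 70 + 35 = 245 (protocol 9.7, SAP 2.13) and the 10% from SAP 2.11.6. The documents give no event rates, so the true rates p below are assumptions. Because 2.11.6 defines no denominator, two readings are shown.

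- Pooled over all patients: 0.10 × 245 = 24.5, so at least 25 patients. Chance = P(X ≥ 25), X ~ Binomial(245, p).
- One arm of 70: 0.10 × 70 = 7 patients. Chance = P(X ≥ 7), X ~ Binomial(70, p).

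| True rate p | Pooled, ≥ 25 of 245 | One arm, ≥ 7 of 70 |
|---|---|---|
| 3% | < 0.0001 | 0.005 |
| 5% | 0.0006 | 0.06 |
| 7% | 0.04 | 0.22 |
| 8% | 0.13 | 0.33 |
| 10% | 0.49 | 0.56 |
| 12% | 0.83 | 0.75 |

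A true excess on active treatment helps little under the pooled reading. With X the sum of Binomial(70, placebo rate) and Binomial(175, active rate), the chance of 25 or more is 0.012 for 2% against 8%, 0.055 for 3% against 9%, and 0.21 for 5% against 10%.

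**3. Whether the contrast can be computed with few events**

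Hypothetical counts, exact conditional odds ratios as in SAP 3.11.8:

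- 700 mg 6/70, placebo 0/70: odds ratio infinite, 95% CI 1.23 to infinity, p = 0.028. Six is below 7. If 210 mg has at most 6 events and 70 mg at most 3, the total is at most 6 + 0 + 6 + 3 = 15, below 25. The condition then fails under both readings.
- 700 mg 9/70, placebo 3/70, 210 mg 6/70, 70 mg 2/35: 20/245 = 8.2%. For 700 mg against placebo the odds ratio is 3.27 (0.77 to 19.63). The pooled condition fails; read per arm, 9/70 = 12.9% meets it.
- All active 23/175, placebo 1/70: 24/245 = 9.8%. The odds ratio is 10.4 (1.6 to 436), p = 0.004. The pooled condition fails; 23/175 = 13.1%, so at least one active arm exceeds 10%.

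The exact method already in the SAP therefore handles such counts. The last two examples also show that the undefined denominator can decide whether a contrast appears.

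**The case against.** The strongest reply is that the SAP does not settle on dropping the contrast. Section 3.11.8 states without condition that odds ratios with intervals will be derived for cardiac, orthopedic and special-interest events. That stands: the documents show an unreconciled conflict. It does not remove the problem, because 2.11.6 cites 3.11.8 as its method, so the condition may well be meant to decide whether that method is run.

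Three further replies also stand in part:

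- The orthopedic side is weaker. SAP 2.11.6 does not restate the 10% for orthopedic events. The rarity qualifier in protocol 9.5.2.2 most naturally governs which measure is shown, but it could govern whether a contrast is shown at all.
- By-group frequencies, and exposure-adjusted rates for special-interest categories that include cardiac effects and fracture healing, are reported whatever the count. In the 9/70 against 3/70 example both counts would be in the tables.
- The pooled denominator is a reading. The SAP elsewhere uses an any-arm threshold for the most frequent adverse events (2.11.3), so a per-arm reading is open.

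It can also be said that contrasts from few events are imprecise. They are, and a wide exact interval shows it.

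**Conclusion.** SAP 2.11.6 places a 10% condition, with no stated denominator, on the cardiac odds ratio, interval and p-value. This conflicts with protocol 9.5.2.1 and with SAP 3.11.8, and SAP 2.14 does not record it. It probably extends to orthopedic events. For true rates of 5% or less, the contrast would appear with probability of about 0.0006 or less under the pooled reading, and about 0.06 or less for a single arm of 70. These figures rest on assumed event rates and on 245 treated patients in the planned split.

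A reader might infer that the SAP suppresses all reporting of rare harms, or that the protocol promised unconditional contrasts for both event classes. The documents do not support either. Frequencies and rates remain, 3.11.8 sets no threshold, and the only clearly unconditional promise is the cardiac relative risk. The point is worth acting on because a protocol-specified safety estimate would usually be lost if 2.11.6 governs.

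**What to change.** - Delete the 10% condition for the contrasts in SAP 2.11.6, and make 2.11.6 and 3.11.8 say the same thing.
- For cardiac events, always report the relative risk against placebo with a 95% confidence interval for each dose, as in protocol 9.5.2.1.
- For orthopedic events, always report the odds ratio and/or risk difference with a 95% confidence interval, as in protocol 9.5.2.2, and state the orthopedic rule explicitly.
- Use exact methods when counts are small. The protocol does not specify this, but 3.11.8 already does for odds ratios.
- Keep a threshold only for Kaplan-Meier estimates and the log-rank test, and define its denominator.
- Record in SAP 2.14 any departure that remains, including odds ratio in place of relative risk if that is kept.

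The cost is edits to these SAP sections and a few table rows. No new data are needed.
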